The primary outcome measure will be rates of risky drinking (i.e., more than 4 drinks at any one sitting or more than 14 drinks/week for men; more than 2 drinks at any one sitting or more than 7 drinks/week for women) within each follow-up period (e.g., months 1-3, 4-6, 7-9, 10-12, 13-18), as determine by the TLFB. Secondary outcomes in the study will be self-reported frequency of heavy drinking days (TLFB), biological measures of alcohol use (%dCDT and GGT), urine toxicology tests to assess other drug use, VA medical records of opioid overdoses, depression, and pain. Outcome data will be analyzed using mixed effect regressions for continuous and categorical data (i.e., SAS) and various packages to examine mediation effects (i.e., MPlus). The alpha level for the primary outcome will be set at 5%.

Data quality will be monitored by random inspection of the completed forms by the research coordinator and any problems detected will be discussed with the PI. The Research prevention counselors will receive standardized training on the interventions, which are all manualized. Adherence to the manuals will be monitored using audiotapes and individual supervision provided by the clinical coordinator. If drift is observed the counselors will be re-trained.

Blind interim analyses of the data will be conducted at two points when 50 and 75% of the sample has been accrued. If the results show statistically overwhelming significant differences between groups, the study will be stopped (or one of the conditions stopped).

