3. If applicable, define the plan for subjects if research shows results such as:

- 3.1. Depression If depression appears to be an issue for a participant, and they are not already receiving treatment, the research staff will consult with [name] for a consult with the participant and a possible referral.
- 3.2. Suicide Participants who indicate any suicidal ideation will be evaluated by [name], [name], or [name] at the CMCVAMC.
- 3.3. Abuse It is anticipated that the Veterans in our study will be engaging in alcohol or drug abuse. [name] will be consulted in the event there is significant change to the Veterans' use status. If the Veteran is in danger in terms of physical abuse or someone else is in danger due to the Veteran abusing them, [name] will be consulted and the appropriate actions will be taken.

4. Statistical Analysis

- 4.1. Include statistical power calculations and the assumptions made in making these calculations. **We consider the primary hypothesis of risky alcohol use, which compares PI and BIO groups on five repeated binary outcomes. We use the sample size formulae of Diggle et al. We expect to have a 20% dropout rate by month 18, and to see a risky drinking rate of 30%. On the assumption of a within subject correlation of 0.3 (resp. 0.4, 0.5), our sample size of 150 per group provides 80% power for a main effect difference of 30% versus 20% (resp. 30% versus 19%, 30% versus 18%) for the BIO versus PI groups.**

**March 2018 Amendment:** Our original power analysis in the grant was very conservative, as it took into account multiple outcome measures and moderation and mediation analyses. We had our statistician re-run the analyses, focusing on the main effect treatment group comparison with the primary outcome measure. If we calculate sample size needed to have 80% power to find a 15- percentage point difference in rates of risky drinking between the two conditions (e.g., 35% control condition vs. 20% experimental condition on risky drinking rate), we need a total of 136 to 162 veterans (depending on different estimates of the correlation between the outcome measure at different follow-up points). If the effect is slightly larger (e.g., 20 percentage point difference), we only need 72 to 84 veterans in total. Therefore, with a combination of the new design we are confident that we will reach a sample size that will be sufficient to at least examine our primary outcome measure.

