e. Missing values. The mixed effects models will provide valid estimates of treatment efficacy if the missing data meet the ignorable missingness assumption. We will conduct further analyses to assess the sensitivity of our inferences to possible violations of this assumption. First, we will use pattern mixture models (104), defining a categorical variable describing the main patterns of missing data, and including it as a main effect and interaction effect with intervention group in the modes for primary outcomes. Significant differences in the estimated intervention effects across levels of the pattern variable suggest one type of non-ignorable missingness. Second, shared parameter models (104) assume that the repeated responses and repeated binary indicators of missingness have possibly correlated random effects, and significant correlation indicates possible non-ignorability. Finally, semiparametric regression models (106) use inverse probability weighting to extend the validity of GEE models, and provide a different type of sensitivity analysis for the mixed effects models. All three approaches require certain model assumptions, so we will compare the results of the analyses over a range of such assumptions.

X. **Privacy and Confidentiality** (*Privacy refers to persons and to their interest in controlling the access of others to themselves.) (Confidentiality refers to protecting information from unauthorized disclosure or intelligible interception.) (Investigator should contact the Privacy Officer for additional details.)*

1. **Indicate the type of data that will be received by the Principal Investigator. Check all that apply.**

- 1.1.  De-identified – Without any identifiers that could link the data to a specific participant. (Contact Privacy Officer for assistance. If data is coded, it is not considered de-identified.)
- 1.2.  Identified – Linked to a specific participant by identifiers sufficient to identify participants. (See [HIPAA](#) and [Common Rule](#) Criteria for list of identifiers.)
- 1.3.  Coded – Linked to a specific subject by a code rather than a direct identifier. If coded is checked, specify:

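### Two of the three dropout sensitivity analyses are read by statistical significance; the pattern-by-group test has too little power for a null result to reassure, and no departure for unobserved drinking is specified

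*Combined protocol and SAP*

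**What the plan says.** Section W.4.2.e (Missing values) says that the mixed models are valid if missingness is ignorable, and plans three analyses of sensitivity to that assumption.

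- **Pattern mixture.** A categorical missing-data pattern enters the primary-outcome model as a main effect and in interaction with group. The reading is: "Significant differences in the estimated intervention effects across levels of the pattern variable suggest one type of non-ignorable missingness".
- **Shared parameter.** Outcomes and missingness indicators have possibly correlated random effects, and "significant correlation indicates possible non-ignorability".
- **Inverse-probability-weighted GEE.** This is offered as a different type of sensitivity analysis, with no significance criterion.

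The section ends by noting that all three need model assumptions and that results will be compared over a range of them. It does not define the pattern levels, the range, an effect estimate averaged over patterns, or any assumption about drinking in windows that were not observed.

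On the amount of missing data, W.4.1 says: "We expect to have a 20% dropout rate by month 18".

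**The concern.** In a drinking trial the main worry about dropout is that Veterans who return to risky drinking stop attending, perhaps more in one arm. The documents make this plausible. Section O.1 provides for removal of a Veteran whose alcohol use is judged to need more intensive treatment, though it does not say whether this can happen after randomization. The March 2018 amendment records fear that admitting alcohol use could cost a Veteran the opioid prescription. The arms also differ greatly in study contact.

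A significance test is a weak guide here. If it has little power, a non-significant result is the likely outcome whether or not dropout distorts the comparison. Drinking after dropout is also unobserved, so no test on the observed data can settle the question. What a reader needs is the PI minus BIO effect under stated alternatives. The plan does not ask for that under the alternative that matters most: missed windows being risky more often than observed ones.

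**Working it through.** **Inputs from the documents.** Five repeated binary outcomes; within-subject correlation ρ of 0.3, 0.4 or 0.5; 20% dropout; control rate 30% in the first calculation in W.4.1 (150 per group). The March 2018 calculation in W.4.1 uses "35% control condition vs. 20% experimental condition on risky drinking rate". The amendment text in O.1 gives 150 entering treatment and 200 randomized; R.1 adds up to 175 (115 + 60). Alpha is 5% (W.1), sidedness not stated.

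**Assumptions not in the documents.** Two-sided alpha, 1:1 allocation, equal dropout by arm, two patterns (dropout, completer), and k = 1 to 4 windows seen before dropout.

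**The plan's own figure.** For main effects, n per group = [1.96√(2p̄q̄) + 0.84√(p₁q₁+p₂q₂)]² × (1+4ρ)/(5d²), divided by 0.8 for dropout. Setting n = 150 with a 30% control rate gives detectable PI rates of 19.7%, 18.8% and 18.1% at ρ = 0.3, 0.4 and 0.5. These round to the stated 20%, 19% and 18%, so the same variance structure can be used below. (The amended total of 136 to 162 does not follow from these inputs: N/0.8 gives 152 to 207 at 35% versus 20%.)

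**Pattern-by-group interaction, 150 Veterans.** Each arm has 75 × 0.2 = 15 dropouts and 60 completers. With V = p₁q₁ + p₂q₂,

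SE² = V(1+(k−1)ρ)/(15k) + V(1+4ρ)/(5×60), and detectable difference = 2.80 × SE.

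Example at 35%/20%, ρ = 0.4, k = 2: V = 0.2275 + 0.16 = 0.3875. SE² = 0.3875×1.4/30 + 0.3875×2.6/300 = 0.01808 + 0.00336 = 0.02144, so SE = 0.146 and the detectable difference is 41 points.

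Detectable difference in points at 35%/20%:

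| Windows seen | ρ 0.3 | ρ 0.4 | ρ 0.5 |
|---|---|---|---|
| 1 | 47 | 48 | 48 |
| 2 | 39 | 41 | 43 |
| 3 | 36 | 38 | 41 |
| 4 | 34 | 37 | 40 |

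Other rates give 34–47 (30%/20%), 36–50 (30%/30%) and 37–52 (35%/35%). The overall range is 34 to 52 points, with SE from 0.120 to 0.187.

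**Power for a 15-point difference** (15 points in completers, none in dropouts) is Φ(0.15/SE − 1.96) + Φ(−0.15/SE − 1.96). SE 0.187 gives 0.124 + 0.003 = 13%; SE 0.120 gives 0.238 + 0.001 = 24%. At 35%/20% alone it is 14–23%. A simulation (400 runs per scenario, ρ = 0.4) gave 19%. For a 30-point difference at 35%/20%, power is 41–69% (49% simulated).

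**Other sizes, 35%/20%.** The detectable difference is 32–45 points at 175, 30–42 at 200 and 24–34 at 300.

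**What a stated departure would show.** Take one window with 20% missing and the planned rates among those observed. Missing = risky in both arms gives 0.8×35 + 20 = 48% for BIO and 0.8×20 + 20 = 36% for PI, so 12 of the 15 points remain. Applied to PI only, 36% against 35% removes the effect. These are extremes, not predictions. They show that the answer depends on the departure and on whether it differs by arm.

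**The case against.** The strongest defence is that the plan sets no significance rule for robustness. Its wording is cautious (significance only suggests or indicates possible non-ignorability), the weighted GEE yields an alternative effect estimate with no test, and the section commits to comparing results over a range of assumptions. All of that stands. A reader might infer that a non-significant test would be taken as proof of robustness, or that the plan has no way to examine robustness. The text supports neither.

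The power figure also has limits. It concerns only the pattern-by-group interaction. The shared-parameter test concerns a correlation between random effects, which cannot be put as a difference in effect, and no power was computed for it. So the inference that both tests will almost always be non-significant is not supported. Dropouts drinking more in both arms alike would appear in the pattern main effect, which the plan includes. Pooled over arms at 30%/30% with one to three windows seen, that contrast has half the interaction SE (0.067 to 0.090) and detects about 19 to 25 points. It is also tempting to say that the detectable interaction exceeds the control rate itself. That is true against 30%, but against 35% the low end, 34 points, falls just short.

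Finally, 150 is one of several sizes in the documents, and the 20% dropout figure was not restated for the amended design. Larger sizes reduce the detectable difference without changing the conclusion.

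These points do not close the gap. Weights built from observed data still assume missingness at random given those data, and the plan states no selection parameter beyond them. The promised range is not specified.

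**Conclusion.** The point holds in a limited form. Two of the three sensitivity analyses are read by significance. For the pattern-by-group interaction the 80%-detectable difference is about 34 to 52 points with 150 Veterans, and power against loss of the whole 15-point effect among dropouts is about 13 to 24%. A null result there is weak evidence of robustness. At 200 randomized the detectable difference is still 30 to 42 points, twice the planned effect or more.

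The figures rest on the assumptions listed in the working. More pattern levels would lower power further, as would the four-window schedule of later enrollees, since completers were given five windows. The remaining defect is one of specification: no effect averaged over patterns, no stated departure for unobserved drinking, and no stated range. It should be corrected, and it can be corrected before analysis.

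**What to change.** Amend W.4.2.e as follows.

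1. Keep the interaction and correlation tests as description, and say that non-significance will not be taken as evidence that missingness is ignorable.
2. Define the pattern levels in advance. Report the PI minus BIO effect with a 95% CI from each sensitivity model, including the pattern-mixture effect averaged over patterns.
3. Add a tipping-point analysis by multiple imputation. Raise the odds of risky drinking in missed windows over a range fixed in advance, equally in both arms and separately by arm, with missing = risky as the extreme. Report the shift at which the primary conclusion changes.
4. Apply step 3 only to scheduled windows that were missed. Veterans enrolled after 4/1/2019 have no 18-month visit (M.3.2 and Study visits), so their 13–18 month window is absent by design and should not be treated as dropout.

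The cost is SAP wording and a standard imputation run, with no new data. The result may look less robust than under the present plan.

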4.3.2.  Discharge date  Admission date  
 4.3.3.  Appointment Dates  Other Dates (e.g. lab tests, x-rays, MRI, etc.)

4.4.  Telephone numbers  
 4.5.  Fax numbers  
 4.6.  Electronic mail addresses  
 4.7.  Social Security/Medical Record Number  
 4.8.  Health plan beneficiary numbers  
 4.9.  Account Numbers  
 4.10.  Certificate/license numbers  
 4.11.  Vehicle identifiers and serial numbers, including license plate numbers  
 4.12.  Device identifiers and serial numbers  
 4.13.  Web universal resource locators (URLS)  
 4.14.  Internet protocol (IP) address numbers  
 4.15.  Biometric identifiers, including fingerprints, voiceprints, audio recordings  
 4.16.  Full-face photographic images and any comparable images  
 4.17.  Any other unique identifying number, characteristic, or code  
 4.18.  Personal and Family History  
 4.19.  History and Physical Examination  Progress Notes  
 4.20.  Discharge Summary(ies)  Photographs, videotapes, other images  
 4.21.  X-Ray  HIV (testing or infectious disease) records  
 4.22.  Diagnostic/Laboratory tests  Sickle cell anemia  
 4.23.  Drug Abuse Information  Behavioral Health notes  
 4.24.  Alcoholism or Alcohol Use  Operative Reports  
 4.25.  Billing records  Medication List  
 4.26.  Health Summary Reports  Anatomic Pathology Report  
 4.27.  Other Records:

5. **Will participants be contacted from existing PHI?**  YES  NO  N/A

5.1. If yes, clearly explain how participants will be contacted (NOTE: this would be the same information as listed under section R.8 identification and recruitment of subjects). **We will use VA VISTA pharmacy records to identify Veterans who are currently being prescribed daily opioid medication for the treatment of chronic pain. Veterans already in addiction treatment will then be excluded from the study. For the remaining patients, the prescribing physicians will be contacted, and notified of our intention to contact the patient to tell him/her about the research study. We will then contact patients via letter to describe the research study and follow-up with a telephone call to invite them to participate.**

**Most often, the BHL refers Veterans to the study team who are engaging in risky drinking, but without the symptomology or levels of consumption that would warrant a referral to a higher level of care, such as the ARU. If during the triage assessment the BHL software flags a Veteran for risky drinking, but not a referral to a higher level of care, then the technician will refer them to the study team.**

6. Provide the titles of the exact individuals who will have access to the collected data. **PI, Research Coordinator, Research Technicians, Data Analyst, Co-Investigator, and Clinical Liaison**

6.1. Explain why these individual will have access to this data. **The PI has access for data safety monitoring. The research coordinator will be collecting and monitoring the data for adherence/accuracy/safety. The Research Technicians will be collecting the data and answering any queries that come up.**

**Y. Information Security (Contact the Information Security Officer for additional assistance regarding confidentiality (storage/security) of research data.)**

1. Provide the precise plan how data is to be collected or acquired (repeat the same information

as listed under “Data Collection” section of this form. **Data will be collected in a private location by research staff. Data collected via paper will be entered into the computer by the researcher. Data collected directly onto the computer will be reviewed by the research staff. The data will be identified using a four digit subject id number. Phone calls between study participants and research counselors will be recorded using a digital recorder. The audio files created from these recordings will be stored on the VA server (<https://vhaphimulh12.v04.med.va.gov/dmumain/>).**

**January 2016 amendment to change data storage location:** Due to a system failure of the MIRECC DMU at the VA, an amendment to this ongoing protocol was made to change where data was stored (as detailed above and in below sections that describe data storage). This is being done with the input from the ISO and PO, and under the current PENN-VA MOU on data storage (even though there is a separate PENN component to our study). The need to use the DMU at Penn is critical because the DMU provides more oversight and protection over the safety and integrity of the data, being able to capture every entry and any changes made. It also keeps the data on a highly secured server to protect not only against hacking, but against catastrophic loss of data.

**We will re-consent current subjects.**

We also note that there was no data loss to due to the VA DMU failure.

**July 2016 Amendment – An amendment to the protocol has been made to change the server back to the secure server at the VA. The reason for this is an issue with software and being able to get through the VA firewall for data entry.**

2. Provide a listing of the exact research data that will be stored, including but not limited to signed, original informed consent and HIPAA authorization forms, case report forms, etc. **Consents, HIPAA authorization, CRFs, blood and urine results, recordings from counseling phone calls. Being entered into DMU will be: dates of research visits, responses to questionnaires and interviews, as well as urine specimen and blood test results.**
3. Indicate how project's research data (original and all copies) will be stored and provide corresponding security systems. **Consents will be kept in binders in locked cabinets within the MIRECC suite at CMCVAMC. Paper Case Report Forms will be kept in a locked drawer in a locked office separate from the consents. All data will be entered into a web-based data entry system on a VA server. In addition, if a Veteran is in the PI condition and has consented to audio recording of their counseling session, we will be using digital recorders to capture the call, and then we will save the audio files of the call to the server (<https://vhaphimulh12.v04.med.va.gov/dmumain/>).**
4. Provide exact location where research data (original and all copies) will be stored and secured. **Data will be stored in the MIRECC Suite, 2nd floor of Bldg 2. Veteran contact data for follow up and tracking purposes will be kept on the research server “[name] – PI with Vets.”**
5. Explain how data is to be transported or transmitted from one location to another. **Phone numbers and participant id numbers will be transmitted to Wellpass through their website ([www.wellpass.com](http://www.wellpass.com)) which will be accessed using a secure CMCVAMC computer and network. Participant id numbers, serum samples, session dates, and blood test results will be transferred to/from MUSC via a password-protected spreadsheet on an encrypted USB device. Data stored on DMU can be entered from the location at which the data is collected. It is transmitted via internet portal.**

5.1. Informed Consent discloses PHI transported or transmitted off-site.  YES  NO  N/A

5.2. HIPAA Authorization discloses entities to whom PHI will be transported or transmitted.  YES  NO  N/A

5.2.1. List all entities or individuals outside CMCVAMC to whom data is to be disclosed, and the justification for such disclosure and the authority. **Blood samples will be sent to MUSC for analysis and will be coded as well. Wellpass (the company that created the SMS text messaging portion of the intervention) will have PHI – telephone numbers – of people randomized to receive the intervention. The Greenphire ClinCard system collects and uses PHI to pay participants.**

5.3. If yes, list the exact data that will be transmitted. **Blood samples with session dates and times and subject ID numbers will be sent to MUSC. Wellpass will receive phone numbers in order to conduct the text messaging portion of the intervention.**

5.4. If yes, explain how data will be protected during transmission outside of CMCVAMC. **Data will be coded with a four digit number. The link to the code will remain at the VA and not used during data analysis**

5.5. Off-site, provide exact location **University of Pennsylvania, [name]; Medical University of South Carolina, [name]; Wellpass, [name]; Greenphire, [name]** (If off-site, attach at least one of the following.)

5.5.1. Data Use/Transfer Agreement  YES  NO  N/A

5.5.2. Off-Site Storage/Transfer of Research Data  YES  NO  N/A

5.5.3. Memorandum of Understanding  YES  NO  N/A

5.5.4. *(Note: VA data disclosed to a non-VA investigator at an academic affiliate for research purposes needs to be approved by the Under Secretary of Health or designee.)*

6. List who is to have access to the data and how they are to access it (anyone who has access to the data is responsible for its security). **PI, co-PI, research coordinator, research technician, research counselor, data analyst**

7. Describe who is to have access and be responsible for the security of the information (e.g., the Coordinating Center, the statistician, and PI who has ultimate responsibility). **PI, co-PI, research coordinator, research technician, research counselor, clinical liaison, data analyst**

8. Provide mechanisms used to account for the information. **There is an electronic record of changes to the data that is stored in the web-based CMCVAMC DMU system. The research coordinator will be responsible for the day-to-day keeping of the information.**

9. Give security measures that must be in place to protect individually identifiable information if collected or used. **PII will be kept locked at the MIRECC Suite, Building 2.**

10. How and to whom a suspected or confirmed loss of VA information is to be reported.

10.1. **The Investigator will notify the Information Security Officer, Privacy Officer, IRB, Associate Chief of Staff for Research and Research Compliance Officer within one hour of a suspected or confirmed loss of VA information.**

11. Identify any circumstances that may warrant special safeguards to protect the rights and welfare of subjects who are likely to be vulnerable including, but not limited to, those subjects who may be susceptible to coercion or undue influence, and describe appropriate actions to provide such safeguards. **N/A**

12. Electronic PHI will be stored on the following:

- 12.1. CMCVAMC desktop computer with password protection and/or encryption.  YES  NO  N/A
  - 12.1.1. If yes, identify where the desktop is located.
- 12.2. CMCVAMC secure server.  YES  NO  N/A
  - 12.2.1. If yes, identify the CMCVAMC server. **MIRECC research server "[name] - PI with Vets"** <https://vhaphimulh12.v04.med.va.gov/dmumain/>
  - 12.2.2. External drive that is password protected and/or encrypted.  YES  NO  N/A
    - 12.2.2.1. If yes, identify the external drive.
- 12.3. Off-Site server  YES  NO  N/A (If off-site, attach at least one of the following.)
  - 12.3.1. Provide exact location and the name of the off-site server
  - 12.3.2. Data Use/Transfer Agreement  YES  NO  N/A
  - 12.3.3. Off-Site Storage/Transfer of Research Data  YES  NO  N/A
  - 12.3.4. Memorandum of Understanding  YES  NO  N/A

13. Explain how data is to be transported or transmitted from one location to another. **Phone numbers and participant id numbers will be transmitted to Wellpass via a password-protected spreadsheet on an encrypted USB device. Participant id numbers, serum samples, session dates, and blood test results will be transferred to/from MUSC via a password-protected spreadsheet on an encrypted USB device. Electronic research data will be transmitted to the VA server via a web-based data entry system on the VA's intranet.**

14. Informed Consent discloses PHI transported or transmitted off-site.  YES  NO  N/A

15. HIPAA Authorization discloses entities to whom PHI will be transported or transmitted.  YES  NO  N/A

16. List all entities or individuals outside CMCVAMC to whom data is to be disclosed, and the justification for such disclosure and the authority. **Blood samples will be sent to MUSC for analysis and will be coded as well. Wellpass (the company that created the SMS text messaging portion of the intervention) will also have PHI – telephone numbers – of people randomized to receive the intervention. The Greenphire ClinCard system collects and uses PHI to pay participants.**

17. Clarify what protection exists for a database. **The web-based DMU system is double password protected and on a secure VA server.**

- 17.1. Data is stored:
  - 17.1.1. With identifiers -  YES  NO
  - 17.1.2. Coded -  YES  NO
  - 17.1.3. De-Identified -  YES  NO
  - 17.1.4. Provide the exact list of identifiers that will be stored. **Dates of research visits**

18. Describe the plan for protecting research data from improper use or disclosure. **All staff will be sufficiently trained on the proper use of data and how to guard against improper use or disclosure.**

- 18.1. The Investigator must notify the Information Security Officer, Privacy Officer, IRB, Associate Chief of Staff for Research and Research Compliance Officer within one hour of the improper use or disclosure.

19. Is there a plan to apply for a Certificate of Confidentiality?  YES  NO  N/A

- 19.1. If yes, provide a copy of the certificate with this application or to the IRB Office as soon as received.
20. **Record Retention:**
  - 20.1. The required records, including the investigator's research records, must be retained until disposition instructions are approved by the National Archives and Records Administration and are published in VHA's Records Control Schedule (RCS 10-1). VHA Handbook 1200.05 §26.h
  - 20.2. Until a schedule for local research records is published, ALL records including identifiers must be retained." ORO/ORD Guidance on Informed Consent Form Modifications Addressing VA Record Retention Requirements (July 23, 2009)
  - 20.3. If there are additional procedures for record retention, explain further. **N/A**

